Gastrointestinal system comprises of more than 200 m² of mucosal surface. The immune system in gastrointestinal mucosa has been studied extensively until this day. The microflora or the microorganism in gastrointestinal system, also commonly known as the gut microbiome, is a part of the immunity system in gastrointestinal mucosa. Around 20% of malignancy are linked to microorganism. The gut microbiome is suspected to have a role in genetic and epigenetic changes that cause dysplasia, clonal expansion, tumor growth, and cancer. In addition, chronic

inflammation is also suspected to have a role in colorectal carcinogenesis. One of the chronic inflammation markers linked with carcinogenesis is NF- κ B.

Several studies showed that dysbiosis or imbalance of gut microbiome is linked with mucosal barrier damage, chronic inflammation and production of carcinogenic metabolite causing neoplasm. Thus far, the association between gut microbiome and colorectal cancer has provided an opportunity to develop new strategies in the screening method of colorectal cancer.

Non-invasive methods for colorectal cancer screening are currently being developed to replace colonoscopy. One of the screening methods is *fecal immunochemical test* (FIT) using fecal samples. This method has a sensitivity of 87.5% in detecting colorectal cancer cases. Another screening method uses blood sample to evaluate *carcinoembryonic antigen* (CEA) level in blood serum. An increase in CEA serum level of more than 5 ng/mL is found in 17-47% of colorectal patients and is associated with poor prognosis.

Research Objectives

General Objectives

To investigate the role of gut microbiome pattern and inflammation marker NF- κ B in colorectal cancer patients

Specific Objectives

1. To obtain data on gut microbiome pattern on young-onset colorectal cancer patients and colorectal cancer patients aged >50 years old.
2. To explore the role of inflammation marker NF- κ B on young-onset colorectal cancer patients and colorectal cancer patients aged >50 years old.
3. To obtain CEA values of young-onset colorectal cancer patients and colorectal cancer patients aged >50 years old.
4. To obtain data on gut microbiome which could be used as screening methods in patients suspected with colorectal cancer

Hypothesis

1. There are differences in gut microbiome pattern on young-onset colorectal cancer patients and colorectal cancer patients aged >50 years old compared to healthy individuals
2. There are differences in NF- κ B on young-onset colorectal cancer patients and colorectal cancer patients aged >50 years old compared to healthy individuals
3. There are differences in CEA values on young-onset colorectal cancer patients and colorectal cancer patients aged >50 years old compared to healthy individuals

Research Benefits

For Researchers

Researchers will expand their knowledge on gut microbiome pattern in colorectal cancer patients.

For Institutions

This study will provide a contribution of science in national and international scale. The result of this study could be used as a guideline on utilizing gut microbiome data on colorectal cancer management.

For Communities

The result of this study is expected to improve the management of colorectal cancer as a screening method that would be applicable in daily clinical practice.

METHODOLOGY

Study Design

This is a cross-sectional study.

Time and Place

This study is conducted in [name] Hospital: Digestive Endoscopy Center, Department of Internal Medicine, Department of Clinical Pathology, Department of Anatomical Pathology, and Eijkman Institute of Molecular Biology from May 2019 to May 2022.

Population

Target Population

Patient suspected with colorectal cancer in Indonesia.

Accessible Population

Patients suspected with colorectal cancer who come to Digestive Endoscopy Center in [name] Hospital to conduct colonoscopy procedure and histopathological examination.

Subject Criteria

Inclusion Criteria

1. Age \geq 35 years old
2. Suspected with colorectal cancer and undergoing a colonoscopy procedure
3. No history of colorectal cancer treatment

Exclusion Criteria

1. Unwilling to provide fecal and blood sample
2. Incomplete colonoscopy procedure due to any reasons

Estimated Sample Size

Since this is a pilot study to obtain gut microbiome pattern on colorectal cancer patients, the number of samples is determined by the researchers: 100 subjects for neoplasm and 50 subjects for non-neoplasm (according to histopathology report).

Randomisation

The sampling will not be randomized. All patients suspected with colorectal cancer who come to Digestive Endoscopy Center in [name] Hospital to conduct colonoscopy procedure and histopathological examination who fulfilled the criteria will be recruited for this study and will undergo a series of examinations

Operational Definition

No.	Variable	Definition	Source	Scale
1.	Patient suspected with colorectal cancer	Patient suspected with colorectal cancer by clinician based on clinical findings such as gastrointestinal bleeding, chronic constipation, chronic diarrhea, nonspecific abdominal pain, weight loss, palpable abdominal mass	Clinical judgement	Nominal
2.	Age	Patient's age (in years)	Medical record	
3.	Sex	Patient's sex	Medical record	Nominal
4.	Family history of colorectal cancer in a first-degree relative	First-degree relative: parents, sibling, children	Medical record and history taking	Nominal 1= No 2= Yes
5.	History of smoking	Past or current history of smoking	Medical record and history taking	Nominal 1= No 2= Yes
4.	FIT results	The result of Fecal immunochemical test (FIT)	Fecal immunochemical test (FIT)	Nominal 1= Negative 2= Positive
5.	Gut microbiome results	The result of gut microbiome examination	Next Generation Sequencing (NGS)	Nominal 1: Fusobacterium 2: Bacteroides 3. Lachnospiraceae

6.	NF- κ B results	The results of NF- κ B examination: positive if accumulated score ≥ 3	Examination with immune-histochemical method	Nominal 1= Negative 2= Positive
7.	CEA results	The results of Carcinoembryonic antigen (CEA) examination	Examination with ELISA method	Nominal 1= Negative 2= Positive
7	Histo-pathological results	The results of histopathological examination from biopsy samples are used as gold standard of colorectal cancer diagnosis	Medical record	Nominal 1 = Colorectal cancer 2 = Non-colorectal cancer

Ethical Approval

This study will be obtained ethical approval from the Ethics Committee of Faculty of Medicine, University of Indonesia.

Research Flow

Patients suspected with colorectal cancer who come to Digestive Endoscopy Center in [name] Hospital to conduct colonoscopy procedure and histopathological examination who fulfilled the criteria will be recruited for this study and will undergo a series of examinations. Each patient will be given an explanation of this study and will be asked his/her willingness to participate on this study by signing the informed consent form. Baseline characteristics data will be obtained from medical record. Before the colonoscopy procedure is conducted, each patient will undergo a score assessment, blood sampling, and fecal sampling.

1. Score Assessment

Asia Pacific Colorectal Screening (APCS) is a validated tool to predict the risk of colorectal cancer in asymptomatic Asian population. The scoring system comprises of three categories: low risk (score 0-1), moderate risk (score 2-3) and high risk (score 4-7). Patients with moderate and high risk will undergo further examinations

Table. Asia Pacific Colorectal Screening (APCS).

Risk Factor	Criteria	Score
Age (in years)	< 50	0
	50 – 69	2
	≥ 70	3
Sex	Female	0
	Male	1
Family history of colorectal cancer in a first-degree relative	Absent	0
	Present	2
History of smoking	Never	0
	Current or past	1

2. Blood Sampling

[figure not shown]
Blood samples will be taken before colonoscopy procedure to evaluate the level of serum CEA by ELISA method and to evaluate the presence of NF- κ B by immunohistochemical method.

- a. Carcinoembryonic antigen (CEA) is a well-known marker for colorectal cancer. A pre-treatment serum CEA level of ≥ 5 ng/mL is associated with poor prognosis in colorectal cancer patients.
- b. NF- κ B is a chronic inflammation marker found in colorectal cancer patients

3. Fecal Sampling

Fecal samples will be taken before colonoscopy procedure to be tested for FIT and to evaluate the gut microbiome.

- a. Fecal immunochemical test (FIT) is a recommended screening method for colorectal cancer. Detection of hemoglobin over a certain level in fecal samples indicated a positive FIT. Patients with positive FIT will undergo further examinations.
- b. Gut microbiome examination will be conducted with next generation sequencing (NGS) method.

Blood samples and fecal samples will be tested in Department of Clinical Pathology [name] Hospital, while gut microbiome will be evaluated in Eijkman Institute of Molecular Biology. Colonoscopy procedure will be conducted in Digestive Endoscopy Center [name] Hospital. Histopathological examination be conducted in Department of Anatomical Pathology [name] Hospital. The results of colonoscopy procedures and histopathology report will be obtained from medical record.

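### Hypotheses 1–3 compare cancer patients with healthy individuals, but the study recruits none, and the histopathology groups are split in two different ways

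*Protocol*

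**What the plan says.** The Hypothesis section names healthy individuals as the reference for the microbiome (1), NF-κB (2) and CEA (3). The first ends with "colorectal cancer patients aged >50 years old compared to healthy individuals". The third reads: "There are differences in CEA values on young-onset colorectal cancer patients and colorectal cancer patients aged >50 years old compared to healthy individuals".

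The sections on who enters the study describe a different population:

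- Target Population: "Patient suspected with colorectal cancer in Indonesia".
- Inclusion Criteria, item 2, which applies to every subject: "Suspected with colorectal cancer and undergoing a colonoscopy procedure".
- Randomisation, which holds the recruitment text, names a single source: "All patients suspected with colorectal cancer who come to Digestive Endoscopy Center".
- Operational Definition, row 1, bases suspicion on "clinical findings such as gastrointestinal bleeding, chronic constipation, chronic diarrhea, nonspecific abdominal pain, weight loss, palpable abdominal mass".

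Histopathology is divided in two ways. Estimated Sample Size plans "100 subjects for neoplasm and 50 subjects for non-neoplasm (according to histopathology report". The histopathology row of the Operational Definition table has two codes: "1 = Colorectal cancer 2 = Non-colorectal cancer".

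**The concern.** The reference group named in all three hypotheses is not in the design. A report worded as the hypotheses are would describe as healthy a group of patients who were being investigated for bleeding, altered bowel habit, pain, weight loss or a mass. Those complaints may have non-neoplastic causes that themselves affect gut flora or an inflammation marker. Neither a difference from this group nor a similarity to it speaks directly about healthy people. The protocol nevertheless foresees guideline use and a screening application in daily practice (Research Benefits).

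The second problem is which group a benign neoplasm belongs to. Under the sample size it counts towards the 100; under the variable table it is coded with the comparator. If any neoplasm is benign, the two-level code cannot reproduce the planned 100/50 split, and the non-cancer group mixes patients with and without a neoplasm.

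**Working it through.** **Reference group.** This is a comparison of text. The planned total is 100 + 50 = 150. Inclusion criterion 2 applies to all 150, and no other source of subjects is described, so the number of healthy volunteers planned is 0. The only group that can serve as comparator is the 50 non-neoplasm patients.

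The Research Flow does not rescue the label. It ties further examinations to a moderate or high APCS score and to a positive FIT. If those sentences restrict who is examined, the comparator moves further from healthy people.

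**Group boundary.** The protocol's figures are 100 neoplasm and 50 non-neoplasm. Let b be the number of benign neoplasms among the 100. The protocol gives no value, so b is an assumption shown over a range.

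- Cancers = 100 − b
- Non-cancer group under the two-level code = 50 + b
- Share of that group with a benign neoplasm = b / (50 + b)

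| Assumed b | Cancers | Non-cancer group | Benign share of non-cancer group |
|---|---|---|---|
| 0 | 100 | 50 | 0% |
| 10 | 90 | 60 | 10/60 = 16.7% |
| 20 | 80 | 70 | 20/70 = 28.6% |
| 30 | 70 | 80 | 30/80 = 37.5% |
| 40 | 60 | 90 | 40/90 = 44.4% |

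At b = 0 the two splits agree.

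**Precision if benign neoplasms are kept apart.** NF-κB and CEA are coded positive/negative in the variable table, so a difference in proportions is a natural scale. The worst-case 95% half-width (proportion 0.5 in both groups), with c cancers against 50 comparators, is 1.96 × √(0.25/c + 0.25/50).

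- c = 100: 1.96 × √(0.0025 + 0.005) = 17.0 points
- c = 80: 1.96 × √(0.003125 + 0.005) = 17.7 points
- c = 60: 1.96 × √(0.004167 + 0.005) = 18.8 points

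The hypotheses name two age groups. If each is compared separately, with an assumed 30/70 split between young-onset and over 50:

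- Of 100 cancers (c = 30 and 70): 22.6 and 18.1 points
- Of 60 cancers (c = 18 and 42): 26.9 and 20.5 points

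For comparison, the variable table's cancer/non-cancer split uses all 150 subjects:

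- b = 20 (80 against 70): 1.96 × √(0.25/80 + 0.25/70) = 16.0 points
- b = 40 (60 against 90): 1.96 × √(0.25/60 + 0.25/90) = 16.3 points

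**The case against.** The strongest reply is that this is loose wording in a pilot study. The four specific objectives never mention healthy people, and the fourth concerns patients suspected of colorectal cancer, for whom non-neoplasm patients from the same referrals are a fitting comparator. Population, criteria and recruitment agree with one another; only the label in the hypotheses is out of line. That supports a cheap correction, but the hypotheses still state a conclusion the design cannot deliver. Pilot status explains a sample size chosen without a power calculation, not a reference group that eligibility excludes. A separate analysis plan could not create that group either.

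On the boundary, the sample size sentence opens by describing a pilot in colorectal cancer patients, and the variable table calls histopathology the gold standard for that diagnosis. Neoplasm may therefore simply mean cancer, in which case the numerical effect is zero. This stands as a possible reading, but the protocol does not state it. It is also true that the benign counts and the age split are assumed, and that only the two-level code loses the detail: the histopathology reports in the medical record keep it.

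Two further points stand. Measured against the cancer/non-cancer split, the precision cost of the three-level code is somewhat larger than against the 100/50 split. And describing a true healthy-control group would be another way to resolve the contradiction.

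**Conclusion.** The concern holds and should be corrected before results are reported. The mismatch over healthy individuals is established from the text alone and affects all three hypotheses: none of the 150 planned subjects is a healthy volunteer, so the contrasts must be read as cancer against no neoplasm among patients referred on suspicion.

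The inconsistency in the histopathology split is also established as text. Its numerical effect depends on a count the protocol does not give. It is nil if all 100 neoplasms are cancers; with an assumed 10 to 40 benign, between 17% and 44% of the non-cancer group would have a neoplasm. Those percentages are illustrations, not estimates.

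**What to change.** 1. In Hypotheses 1–3, replace healthy individuals with: patients referred for suspected colorectal cancer who have no neoplasm on complete colonoscopy and histopathology. Limit the conclusions to that population. This fits the exclusion of incomplete colonoscopies. If the sponsor does want a statement about healthy people, a healthy-control group with its own source, criteria and number must be described, which is a larger change.
2. State whether the APCS and FIT sentences in the Research Flow restrict who is examined. If they do, add that restriction to the comparator's label.
3. Code histopathology in three levels: colorectal cancer, benign neoplasm, no neoplasm. Use that classification in the hypotheses, the sample size and the variable table. Keep benign neoplasms out of the no-neoplasm comparator and report them separately.
4. State whether the 100 counts cancers only or all neoplasms.

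**Cost.** Rewording three hypotheses, one extra code level taken from reports already obtained, and a sentence on each of items 2 and 4. No new procedures are needed. More subjects are needed only if the 100 is to mean cancers and some neoplasms prove benign. The claim becomes narrower. If the 100 includes benign neoplasms, precision falls: with an assumed 40 benign, the half-width rises by 1.8 points against the 100/50 split (17.0 to 18.8) and by about 2.4 points against the 60/90 split (16.3 to 18.8; the difference is taken before rounding).

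### Other malignancy, its treatment, and anti-inflammatory or immunosuppressive drugs are neither excluded nor listed as variables in either group, so the CEA and NF-κB contrasts with supposedly healthy comparators may be confounded

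*Protocol*

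**What the plan says.** Under Subject Criteria, the protocol has three inclusion criteria: a minimum age of 35, "Suspected with colorectal cancer and undergoing a colonoscopy procedure", and "No history of colorectal cancer treatment". The two exclusion criteria are "Unwilling to provide fecal and blood sample" and "Incomplete colonoscopy procedure due to any reasons". None concerns other disease or concomitant drugs.

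The Operational Definition table lists the entry findings ("gastrointestinal bleeding, chronic constipation, chronic diarrhea, nonspecific abdominal pain, weight loss, palpable abdominal mass"), age, sex, family history, smoking, FIT, gut microbiome, NF-κB, CEA and histopathology. The last is the gold standard and has two codes, colorectal cancer and non-colorectal cancer. The Estimated Sample Size section plans 100 neoplasm and 50 non-neoplasm subjects, split by the histopathology report.

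Hypothesis 3 reads: "There are differences in CEA values on young-onset colorectal cancer patients and colorectal cancer patients aged >50 years old compared to healthy individuals". Hypothesis 2 makes the same comparison for NF-κB, which the Blood Sampling section says "is a chronic inflammation marker found in colorectal cancer patients".

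**The concern.** The hypotheses name one comparator and recruitment supplies another. Everyone enters because a clinician suspects colorectal cancer, and several entry findings (weight loss, an abdominal mass, chronic diarrhea) are compatible with cancer outside the colon or with colitis. Followed as written, the protocol counts a patient with cancer elsewhere and a benign colon biopsy as non-colorectal cancer, and so as part of the group that stands in for healthy people.

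Two consequences follow. If another cancer can raise CEA, such patients raise comparator positivity and shrink the contrast of Hypothesis 3. Because the protocol treats NF-κB as an inflammation marker, colitis or drugs that act on inflammation may shift it, and with it the contrast of Hypothesis 2. Without a defined item for these exposures, the analysis cannot reliably separate them from the effect of colorectal cancer. This is a matter of what is collected, so an analysis plan cannot repair it later.

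**Working it through.** **The plan's own figure.** The sample of 100 + 50 = 150 is set by the researchers for a pilot study, with no alpha, power or effect size. There is no calculation to reproduce and no arithmetic error.

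**CEA inputs.**
- From the protocol's background: CEA above 5 ng/mL in 17–47% of colorectal cancer patients.
- Assumed: 5% CEA positivity in cancer-free comparators and 40% in comparators with another cancer.
- Assumed: a share *f* of the 50 comparators with another cancer, from 2% (1 patient) to 20% (10 patients).

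**CEA formula.** Comparator positivity = (1 − *f*) × 0.05 + *f* × 0.40. The loss in the difference is therefore *f* × (0.40 − 0.05) = 0.35*f*, whatever the case rate.

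| *f* | Comparator positivity | Points lost | Difference at 17% | Difference at 47% |
|---|---|---|---|---|
| 0 | 5.0% | 0 | 12.0 | 42.0 |
| 0.02 | 0.049 + 0.008 = 5.7% | 0.7 | 11.3 | 41.3 |
| 0.10 | 0.045 + 0.040 = 8.5% | 3.5 | 8.5 | 38.5 |
| 0.20 | 0.040 + 0.080 = 12.0% | 7.0 | 5.0 | 35.0 |

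Relative to the unaffected difference, the loss at 17% is 0.7/12 = 6%, 3.5/12 = 29% and 7/12 = 58%. At 47% it is 0.7/42 = 2%, 3.5/42 = 8% and 7/42 = 17%.

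**Sensitivity to the 40%.** With 30% or 50% in its place, the loss is 0.25*f* or 0.45*f*: 2.5 to 4.5 points at *f* = 0.10, and 5 to 9 points at *f* = 0.20. I also computed the power of a two-proportion test with 50 comparators against 100 cases at an assumed two-sided alpha of 0.05. This treats all 100 neoplasm subjects as one colorectal cancer group, which is generous because the hypotheses name two age groups.
- At 17% case positivity, power is 0.55 with *f* = 0. It is 0.34 to 0.21 with *f* = 0.10, and 0.19 to 0.06 with *f* = 0.20 (30% to 50% positivity in those affected).
- At 47%, power stays at 0.99 or above throughout.

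**NF-κB.** The protocol gives no rates. For illustration, assume 60% positive in cases and 30% in comparators, with positivity halved in drug users.
- No drug use: 60 − 30 = 30 points.
- 20% use in comparators only: 30 × (1 − 0.2 × 0.5) = 27%, so 60 − 27 = 33 points; the contrast widens.
- 20% use in both groups: 60 × 0.9 = 54%, so 54 − 27 = 27 points; the contrast narrows and the ratio stays at 2.0.
- 20% use in cases only: 54 − 30 = 24 points; the contrast narrows further.

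The sign of the change depends on who is exposed, which the protocol gives no defined way of knowing.

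**The case against.** A reader might infer that the distortion falls on the comparator alone, because the treatment criterion names only colorectal cancer. The protocol does not support that. Groups are formed after histopathology, so one set of criteria applies to everyone. A new colorectal cancer patient may equally take aspirin or steroids, or have had another cancer. The treatment criterion also removes previously treated colorectal cancer patients with no current neoplasm, who would otherwise be comparators, so it does not act on cases alone. A predominantly one-sided effect is plausible only for another cancer and CEA, because the comparators are the group meant to be cancer-free.

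A reader might also infer that nothing relevant is recorded. That goes too far. Baseline characteristics, colonoscopy results and the histopathology report all come from the medical record, so colitis seen at biopsy is in a source the study already uses. What is missing is a defined item for other malignancy and for drugs.

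The size is open to challenge too. Only the 17–47% is documented. The 58% loss pairs the largest assumed share with the lowest case rate, and with one affected comparator in 50 the loss is under one point.

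Finally, excluding such patients would sit badly with the target population of suspected cancer and with Specific Objective 4 on screening. Removing subjects for a malignancy found at the index work-up would be exclusion after results are known, and could flatter the markers' specificity. This objection stands, and it points to recording rather than exclusion.

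**Conclusion.** The point holds as a gap in both groups. Other malignancy, its treatment, and anti-inflammatory or immunosuppressive drugs are neither excluded nor listed, while symptomatic comparators stand in for healthy individuals. The CEA contrast may be pulled toward no difference. The NF-κB contrast may be confounded in a direction that cannot be stated in advance.

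Under the assumed 5% and 40% positivity, the CEA loss is about 0.7 to 7 points for a 2–20% share of affected comparators. That matters if case positivity is near 17% and little if it is near 47%. The true share is unknown, so these figures show sensitivity and do not estimate bias. For a pilot study this is a cheap improvement worth making. It does not invalidate the design.

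**What to change.** Add to the Operational Definition table, for all subjects and from medical record and history:

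1. Another active or previously treated malignancy (no/yes), including one found at the index work-up.
2. Current use of a systemic steroid, immunosuppressant, aminosalicylate, or regular NSAID or aspirin (no/yes).
3. A flag for active colitis, taken from the histopathology report.

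Report the CEA and NF-κB contrasts with and without flagged subjects. In Hypotheses 2 and 3, describe the comparator as symptomatic non-neoplasm patients instead of healthy individuals. Excluding another malignancy already known at entry is optional. Subjects should not be excluded because of what the index work-up finds.

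The cost is a protocol amendment, a few extra case-record items (history is already taken for family history and smoking) and one sensitivity analysis. No patient's care changes.

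### Excluding every incomplete colonoscopy drops biopsy-proven cancers that the scope could not pass, so the case group may under-represent obstructing tumours

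*Protocol*

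**What the plan says.** Under Subject Criteria, the second exclusion criterion is "Incomplete colonoscopy procedure due to any reasons". No other section of the protocol restores a subject excluded in this way.

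The other relevant rules are these:

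- **Case status.** The Operational Definition table says: "The results of histopathological examination from biopsy samples are used as gold standard of colorectal cancer diagnosis". Estimated Sample Size likewise forms the two groups (100 neoplasm, 50 non-neoplasm) from the histopathology report. Neither place makes a complete examination part of the definition.
- **Timing.** Research Flow says: "Before the colonoscopy procedure is conducted, each patient will undergo a score assessment, blood sampling, and fecal sampling". The items on blood and fecal sampling repeat this for CEA and NF-κB, and for FIT and the microbiome.
- **Population.** The target population is "Patient suspected with colorectal cancer in Indonesia", with no limit by stage or obstruction. Under Randomisation, all such patients "who fulfilled the criteria will be recruited for this study and will undergo a series of examinations".
- **Grounds for suspicion.** The Operational Definition lists "gastrointestinal bleeding, chronic constipation, chronic diarrhea, nonspecific abdominal pain, weight loss, palpable abdominal mass".

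**The concern.** Whether a colonoscopy is complete is known only once it has been done, after the samples are taken. The criterion therefore selects subjects on the outcome of the diagnostic procedure. Among cancer patients that outcome may depend on the disease itself, because a tumour can stop the scope. Such a tumour can still be biopsied, and the protocol's own definition then makes the patient a case. The exclusion removes that case all the same.

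At stake is what the case group represents. The hypotheses speak of colorectal cancer patients without restriction by extent, and specific objective 4 concerns screening in patients with suspected cancer. If obstructing cancers are dropped, the marker results describe a narrower group. The protocol ties raised CEA to poor prognosis, which is its own reason to think that CEA positivity could differ between excluded and retained cancers.

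**Working it through.** **What follows from the text alone**

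1. A patient with a biopsied cancer and an incomplete examination meets the histological definition of a case (Operational Definition).
2. Blood and stool from that patient already exist ("Blood samples will be taken before colonoscopy procedure to evaluate the level of serum CEA by ELISA method"; "Fecal samples will be taken before colonoscopy procedure to be tested for FIT and to evaluate the gut microbiome").
3. Exclusion 2 removes the patient whatever the reason for incompletion.
4. The listed symptoms include constipation, weight loss and a palpable mass, so bulky or obstructing tumours are to be expected among those recruited.

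Steps 1 to 3 are textual. Step 4, and the link from obstruction to incompletion, are clinical inference.

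**Size**

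The protocol has no figure of its own to reproduce. Its sample size is set by the researchers without a formula and is not in dispute here.

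Let s be the share of confirmed cancers excluded, and d the marker positivity in excluded cancers minus that in retained cancers. Then:

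- overall positivity = (1 − s) × retained + s × (retained + d) = retained + s × d
- bias in the reported case positivity = −s × d

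The documents give neither s nor d, so both are assumed. The starting value of 47% is the upper end of the range for raised CEA in the protocol's background text.

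| s (assumed) | d = 0 | d = 20 points | d = 30 points | Retained CEA positivity if overall is 47% (d = 20; 30) |
|---|---|---|---|---|
| 5% | 0 | −1.0 | −1.5 | 46%; 45.5% |
| 10% | 0 | −2.0 | −3.0 | 45%; 44% |
| 20% | 0 | −4.0 | −6.0 | 43%; 41% |

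*A wider set of assumptions.* Take 10–30% of cancers excluded, positivity of 60–75% in these, and 17–47% in retained cancers. The smallest bias is 0.10 × (60 − 47) = 1.3 points. The largest is 0.30 × (75 − 17) = 17.4 points. The protocol's 17–47% refers to colorectal patients overall, so using it for retained cancers only is a further assumption.

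*FIT.* Start from the 87.5% sensitivity in the background text and assume that FIT is positive in every excluded cancer. Retained sensitivity is (0.875 − s) / (1 − s): 86.8%, 86.1% and 84.4% for s = 5%, 10% and 20%.

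*Recruitment.* If all 100 neoplasm subjects were cancers, retaining 100 would take 100 / (1 − s) confirmed cases: about 106, 112 and 125.

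**The case against.** The strongest reply is that a complete examination secures correct classification and that one entry rule for everyone is cleaner than two. The first part stands for subjects classified as non-cancer: an incomplete examination cannot rule out a lesion further on. It also stands for a subject with only a benign neoplasm, because the Operational Definition codes histology as cancer or non-cancer and an unseen cancer would be coded wrongly. Any exemption must therefore stop at biopsy-proven cancer. For such a cancer, nothing beyond the obstruction can change case status, so a completeness rule that differs by group is justified.

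Some further objections also stand:

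- The word incomplete is not defined in the protocol. Taking it to cover a scope stopped by a tumour is an interpretation, though the breadth of the criterion supports it.
- The loss matters less for a screening use aimed at early, non-obstructing cancers, although objective 4 names suspected patients.
- Reporting of exclusions and sensitivity analyses may sit in an SAP that is not shown. Eligibility, however, is fixed here, and an analysis plan does not restore subjects whom the criterion excludes.

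A reader might infer more than the documents support:

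- **That only cases are affected.** The non-neoplasm group also comes from symptomatic patients, so disease-related incompletion cannot be ruled out there.
- **That every marker comparison is biased in a known direction.** Only CEA has a direction suggested by the protocol. That direction would shrink the case-control contrast and would not create a false difference.
- **That a fixed number of points is lost.** No incompletion rate or marker difference is given.
- **That the excluded share applies to everyone enrolled.** It applies to confirmed cancers only. If the neoplasm group includes adenomas, the effect on that group is diluted.

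**Conclusion.** The point holds as a limited selection problem. As written, the criterion discards biopsy-proven, already sampled cancers for a reason plausibly tied to tumour extent. The results would then describe cancers with a completed examination, which is narrower than the stated target population.

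That the criterion excludes such patients follows from the text. That obstructing cancers are selectively lost rests on clinical inference, and the amount rests on assumed inputs. On moderate assumptions CEA positivity in cases is understated by about 1 to 6 points. The most extreme inputs give about 17 points, and there is no bias if positivity is equal in excluded and retained cancers. For NF-κB and the microbiome neither size nor direction can be stated. In a pilot whose sample size was set without a power calculation, this is minor to moderate: worth correcting because the correction is cheap, but no ground to call the comparisons invalid.

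**What to change.** Reword exclusion criterion 2 as: *Incomplete colonoscopy without a histological diagnosis of colorectal cancer.*

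- Keep biopsy-proven cancers whatever the extent of the examination.
- Keep the complete-colonoscopy requirement for every subject classified as non-cancer, including those with only a benign neoplasm.
- Record the reason for each incomplete examination.
- Report a sensitivity analysis restricted to complete examinations.

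The cost is a one-line eligibility amendment and a few more assays on samples already taken. The downsides are small: synchronous lesions beyond the obstruction go unseen in retained cases, and completeness requirements differ by group. The sensitivity analysis shows whether the retained cases change the results. If the criterion is left as it is, the protocol should at least state that its results apply to cancers with a completed colonoscopy.
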